4.9 Monitoring of the Study

At regular intervals during the study, a representative of an independent monitoring company selected by Alliance Pharmaceuticals Ltd. (Onorach Limited) will visit the study centre. At each monitoring visit, the Investigator and the monitor will review study progress, compliance with the study protocol, CRF's, and any emergent problems.

4.10 Quality Assurance

In accordance with Good Clinical Practice Guidelines and recommendations, Alliance Pharmaceuticals Ltd. may undertake an independent quality assurance audit of the clinical study and related documentation during the course of this study. The purpose of the audit is to determine whether the evaluated trial related activities were conducted, and the data were recorded, analysed and accurately reported according to the protocol, Alliance Pharmaceuticals Ltd.'s Standard Operating Procedures, Good Clinical Practice and the applicable regulatory requirements. At any stage during the

study, the Investigator has the responsibility to make all data available to Alliance Pharmaceuticals Ltd. and/or relevant authority (where required) for auditing purposes. Such audits will at all times be conducted in accordance with national, legal and ethical requirements.

4.11 Protocol Appendices

It is specified that the appendices attached to this protocol and referred to in the main text of this protocol form an integral part of the protocol.

4.12 Protocol Amendments

Neither Alliance Pharmaceuticals Ltd. nor the Investigators nor the Clinical Research Organisation may make any changes or amendments to this protocol, after the protocol has been agreed and signed by all parties, unless such change(s) or amendment(s) have been fully discussed and agreed by both the Investigator and Alliance Pharmaceuticals Ltd. Any change or amendment agreed will be recorded in writing, the written amendment will be signed by the Investigator and by Alliance Pharmaceuticals Ltd. and the signed amendment will be appended to this protocol.

4.13 Research Registration and Publication Policy

This study will be registered in a publicly accessible database before enrolment of the first research participant.

Submission of study results for publication will not take place without prior discussion with Alliance Pharmaceuticals Ltd., allowing the company sufficient time to analyse such results and provide written agreement to publication, which will not be unreasonably withheld. Alliance Pharmaceuticals Ltd. reserves the right to use the results and reports of this study for any purpose.

4.14 Early Termination of the Study

By agreement between Alliance Pharmaceuticals Ltd. and the Principal Investigators, the study may be terminated at any time if the recruitment rate is such that the required number of participants will not be recruited within the specified time, if the products being used are deemed to be failing unacceptably, or if any safety concerns arise.

Table 1: Schedule of Events

| Day | Screening | 0 | 1 | 2 | 3 | 4 | 5 | 6 | 7 | 8 | 9 | 10 | 11 | 12 | 13 | 14 |
|---|-----------|---|---|---|---|---|---|---|---|---|---|----|----|----|----|----|
| Provide Patient Information Booklet | х | | | | | | | | | | | | | | | |
| Eligibility | х | | | | | | | | | | | | | | | |
| Screen Index Case(s) for Active Lice Infestation (at Day 6 only if infested at Day 3) | | х | | | х | | | х | | | | | | | | |
| Inclusion/Exclusion Criteria Assessment | | х | | | | | | | | | | | | | | |
| Informed Consent | | х | | | | | | | | | | | | | | |
| Demographics | | х | | | | | | | | | | | | | | |
| Medical & Family History | | х | | | | | | | | | | | | | | |
| Treat Index Case(s) (only if infestation is still active after Day 0) | | х | | | х | | | Х | | | | | | | | |
| Instruction in use of Shampoo & Patient Diary | | х | | | | | | | | | | | | | | |
| Supply Shampoo | | х | | | | | | | | | | | | | | |
| Participants Record use of Shampoo in Patient Diary | | х | Х | Х | х | Х | х | Х | х | Х | Х | х | х | х | х | |
| Participants Screened for Active Lice Infestation | | | | | | | | | | | | | | | | х |
| Record Safety Data | | | | | | | | | | | | | | | | х |
| Collect User Acceptability Data | | | | | | | | | | | | | | | | х |
| Collect Patient Diaries | | | | | | | | | | | | | | | | х |
| Collect Excess Shampoo | | | | | | | | | | | | | | | | х |
| Study Completion Form | | | | | | | | | | | | | | | | х |
| | | | | | | | | | | | | | | | | |
| | | | | | | | | | | | | | | | | |
| | | | | | | | | | | | | | | | | |
| VAM2301 Protocol: Version: 2.1, dated 3rd November 2021 | | | | | | | | | | | | | | | | |

5. Appendix 1: Declaration of Helsinki

WORLD MEDICAL ASSOCIATION DECLARATION OF HELSINKI

Ethical Principles for Medical Research Involving Human Subjects

Adopted by the 18th WMA General Assembly, Helsinki, Finland, June 1964 and amended by the:

29th WMA General Assembly, Tokyo, Japan, October 1975

35th WMA General Assembly, Venice, Italy, October 1983

41st WMA General Assembly, Hong Kong, September 1989

48th WMA General Assembly, Somerset West, Republic of South Africa, October 1996

52nd WMA General Assembly, Edinburgh, Scotland, October 2000

53rd WMA General Assembly, Washington, DC, USA, October 2002 (Note of Clarification on paragraph 29 added)

55th WMA General Assembly, Tokyo, Japan, October 2004 (Note of Clarification on Paragraph 30 added)

59th WMA General Assembly, Seoul, Korea, October 2008

64th WMA General Assembly, Fortaleza, Brazil, October 2013

Preamble

1. The World Medical Association (WMA) has developed the Declaration of Helsinki as a statement of ethical principles for medical research involving human subjects, including research on identifiable human material and data.

The Declaration is intended to be read as a whole and each of its constituent paragraphs should be applied with consideration of all other relevant paragraphs.

2. Consistent with the mandate of the WMA, the Declaration is addressed primarily to physicians. The WMA encourages others who are involved in medical research involving human subjects to adopt these principles.

General Principles

3. The Declaration of Geneva of the WMA binds the physician with the words, "The health of my patient will be my first consideration," and the International Code of Medical Ethics declares that, "A physician shall act in the patient's best interest when providing medical care."

- 4. It is the duty of the physician to promote and safeguard the health, well-being and rights of patients, including those who are involved in medical research. The physician's knowledge and conscience are dedicated to the fulfilment of this duty.
- 5. Medical progress is based on research that ultimately must include studies involving human subjects.
- 6. The primary purpose of medical research involving human subjects is to understand the causes, development and effects of diseases and improve preventive, diagnostic and therapeutic interventions (methods, procedures and treatments). Even the best proven interventions must be evaluated continually through research for their safety, effectiveness, efficiency, accessibility and quality.
- 7. Medical research is subject to ethical standards that promote and ensure respect for all human subjects and protect their health and rights.
- 8. While the primary purpose of medical research is to generate new knowledge, this goal can never take precedence over the rights and interests of individual research subjects.
- 9. It is the duty of physicians who are involved in medical research to protect the life, health, dignity, integrity, right to self-determination, privacy, and confidentiality of personal information of research subjects. The responsibility for the protection of research subjects must always rest with the physician or other health care professionals and never with the research subjects, even though they have given consent.
- 10. Physicians must consider the ethical, legal and regulatory norms and standards for research involving human subjects in their own countries as well as applicable international norms and standards. No national or international ethical, legal or regulatory requirement should reduce or eliminate any of the protections for research subjects set forth in this Declaration.
- 11. Medical research should be conducted in a manner that minimises possible harm to the environment.
- 12. Medical research involving human subjects must be conducted only by individuals with the appropriate ethics and scientific education, training and qualifications. Research on patients or healthy volunteers requires the supervision of a competent and appropriately qualified physician or other health care professional.
- 13. Groups that are underrepresented in medical research should be provided appropriate access to participation in research.
- 14. Physicians who combine medical research with medical care should involve their patients in research only to the extent that this is justified by its potential preventive, diagnostic or therapeutic value and if the physician has good reason to believe that

participation in the research study will not adversely affect the health of the patients who serve as research subjects.

15. Appropriate compensation and treatment for subjects who are harmed as a result of participating in research must be ensured.

Risks, Burdens and Benefits

16. In medical practice and in medical research, most interventions involve risks and burdens.

Medical research involving human subjects may only be conducted if the importance of the objective outweighs the risks and burdens to the research subjects.

17. All medical research involving human subjects must be preceded by careful assessment of predictable risks and burdens to the individuals and groups involved in the research in comparison with foreseeable benefits to them and to other individuals or groups affected by the condition under investigation.

Measures to minimise the risks must be implemented. The risks must be continuously monitored, assessed and documented by the researcher.

18. Physicians may not be involved in a research study involving human subjects unless they are confident that the risks have been adequately assessed and can be satisfactorily managed.

When the risks are found to outweigh the potential benefits or when there is conclusive proof of definitive outcomes, physicians must assess whether to continue, modify or immediately stop the study.

Vulnerable Groups and Individuals

19. Some groups and individuals are particularly vulnerable and may have an increased likelihood of being wronged or of incurring additional harm.

All vulnerable groups and individuals should receive specifically considered protection.

20. Medical research with a vulnerable group is only justified if the research is responsive to the health needs or priorities of this group and the research cannot be carried out in a non-vulnerable group. In addition, this group should stand to benefit from the knowledge, practices or interventions that result from the research.

Scientific Requirements and Research Protocols

21. Medical research involving human subjects must conform to generally accepted scientific principles, be based on a thorough knowledge of the scientific literature, other

relevant sources of information, and adequate laboratory and, as appropriate, animal experimentation. The welfare of animals used for research must be respected.

22. The design and performance of each research study involving human subjects must be clearly described and justified in a research protocol.

The protocol should contain a statement of the ethical considerations involved and should indicate how the principles in this Declaration have been addressed. The protocol should include information regarding funding, sponsors, institutional affiliations, potential conflicts of interest, incentives for subjects and information regarding provisions for treating and/or compensating subjects who are harmed as a consequence of participation in the research study.

In clinical trials, the protocol must also describe appropriate arrangements for post-trial provisions.

Research Ethics Committees

23. The research protocol must be submitted for consideration, comment, guidance and approval to the concerned research ethics committee before the study begins. This committee must be transparent in its functioning, must be independent of the researcher, the sponsor and any other undue influence and must be duly qualified. It must take into consideration the laws and regulations of the country or countries in which the research is to be performed as well as applicable international norms and standards but these must not be allowed to reduce or eliminate any of the protections for research subjects set forth in this Declaration.

The committee must have the right to monitor ongoing studies. The researcher must provide monitoring information to the committee, especially information about any serious adverse events. No amendment to the protocol may be made without consideration and approval by the committee. After the end of the study, the researchers must submit a final report to the committee containing a summary of the study's findings and conclusions.

Privacy and Confidentiality

24. Every precaution must be taken to protect the privacy of research subjects and the confidentiality of their personal information.

Informed Consent

25. Participation by individuals capable of giving informed consent as subjects in medical research must be voluntary. Although it may be appropriate to consult family members or community leaders, no individual capable of giving informed consent may be enrolled in a research study unless he or she freely agrees.

26. In medical research involving human subjects capable of giving informed consent, each potential subject must be adequately informed of the aims, methods, sources of funding, any possible conflicts of interest, institutional affiliations of the researcher, the anticipated benefits and potential risks of the study and the discomfort it may entail, post-study provisions and any other relevant aspects of the study. The potential subject must be informed of the right to refuse to participate in the study or to withdraw consent to participate at any time without reprisal. Special attention should be given to the specific information needs of individual potential subjects as well as to the methods used to deliver the information.

After ensuring that the potential subject has understood the information, the physician or another appropriately qualified individual must then seek the potential subject's freely given informed consent, preferably in writing. If the consent cannot be expressed in writing, the non-written consent must be formally documented and witnessed.

All medical research subjects should be given the option of being informed about the general outcome and results of the study.

- 27. When seeking informed consent for participation in a research study the physician must be particularly cautious if the potential subject is in a dependent relationship with the physician or may consent under duress. In such situations the informed consent must be sought by an appropriately qualified individual who is completely independent of this relationship.
- 28. For a potential research subject who is incapable of giving informed consent, the physician must seek informed consent from the legally authorised representative. These individuals must not be included in a research study that has no likelihood of benefit for them unless it is intended to promote the health of the group represented by the potential subject, the research cannot instead be performed with persons capable of providing informed consent, and the research entails only minimal risk and minimal burden.
- 29. When a potential research subject who is deemed incapable of giving informed consent is able to give assent to decisions about participation in research, the physician must seek that assent in addition to the consent of the legally authorised representative. The potential subject's dissent should be respected.
- 30. Research involving subjects who are physically or mentally incapable of giving consent, for example, unconscious patients, may be done only if the physical or mental condition that prevents giving informed consent is a necessary characteristic of the research group. In such circumstances the physician must seek informed consent from the legally authorised representative. If no such representative is available and if the research cannot be delayed, the study may proceed without informed consent provided that the specific reasons for involving subjects with a condition that renders them unable to give informed consent have been stated in the research protocol and the study has been approved by a research ethics committee.

Consent to remain in the research must be obtained as soon as possible from the subject or a legally authorised representative.

- 31. The physician must fully inform the patient which aspects of their care are related to the research. The refusal of a patient to participate in a study or the patient's decision to withdraw from the study must never adversely affect the patient-physician relationship.
- 32. For medical research using identifiable human material or data, such as research on material or data contained in biobanks or similar repositories, physicians must seek informed consent for its collection, storage and/or reuse. There may be exceptional situations where consent would be impossible or impracticable to obtain for such research. In such situations the research may be done only after consideration and approval of a research ethics committee.

Use of Placebo

33. The benefits, risks, burdens and effectiveness of a new intervention must be tested against those of the best proven intervention(s), except in the following circumstances:

Where no proven intervention exists, the use of placebo, or no intervention, is acceptable; or

Where for compelling and scientifically sound methodological reasons the use of any intervention less effective than the best proven one, the use of placebo, or no intervention is necessary to determine the efficacy or safety of an intervention

and the patients who receive any intervention less effective than the best proven one, placebo, or no intervention will not be subject to additional risks of serious or irreversible harm as a result of not receiving the best proven intervention.

Extreme care must be taken to avoid abuse of this option.

Post-Trial Provisions

34. In advance of a clinical trial, sponsors, researchers and host country governments should make provisions for post-trial access for all participants who still need an intervention identified as beneficial in the trial. This information must also be disclosed to participants during the informed consent process.

Research Registration and Publication and Dissemination of Results

- 35. Every research study involving human subjects must be registered in a publicly accessible database before recruitment of the first subject.
- 36. Researchers, authors, sponsors, editors and publishers all have ethical obligations with regard to the publication and dissemination of the results of research. Researchers have a duty

to make publicly available the results of their research on human subjects and are accountable for the completeness and accuracy of their reports. All parties should adhere to accepted guidelines for ethical reporting. Negative and inconclusive as well as positive results must be published or otherwise made publicly available. Sources of funding, institutional affiliations and conflicts of interest must be declared in the publication. Reports of research not in accordance with the principles of this Declaration should not be accepted for publication.

Unproven Interventions in Clinical Practice

37. In the treatment of an individual patient, where proven interventions do not exist or other known interventions have been ineffective, the physician, after seeking expert advice, with informed consent from the patient or a legally authorised representative, may use an unproven intervention if in the physician's judgement it offers hope of saving life, reestablishing health or alleviating suffering. This intervention should subsequently be made the object of research, designed to evaluate its safety and efficacy. In all cases, new information must be recorded and, where appropriate, made publicly available.

6. APPENDIX 2: ISO 14155:2020 CLINICAL INVESTIGATION OF MEDICAL DEVICES FOR HUMAN USE – GOOD CLINICAL PRACTICE

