2.3.3.4 Use of Patient Diaries During the Study (Days 1-14)

During the study, participants or their care givers will record information in the patient diary on when the shampoo was used. They will also record any adverse events at the time of occurrence.

2.3.3.5 Final Follow up Assessment (Day 14, +1 day).

At the end of the 14 day follow up period, the investigator will conduct the final assessment, unless the participant is withdrawn sooner, i.e. they choose to withdraw or are withdrawn on safety grounds. At the final assessment, all participants' hair will be combed with the head louse detection comb and any lice found will be taped (with clear tape) into the participant's CRF. If any participants, or non-participating household members, have live lice at the end of the study they will be offered a standard of care treatment (Vamousse Treatment Mousse).

All adverse events and changes in concomitant medication at any point during the study will be recorded in the CRF. Patient diaries will be collected.

Any remaining supply of investigational product will be collected by the investigator.

The Completion/Withdrawal Form will then be completed.

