2.3.7 Withdrawals

Participants may be withdrawn from the study at any time for the following reasons:

Adverse Event:

The participant is withdrawn from the study by the Investigator because of an adverse event, whether or not the Investigator believes it to be serious or caused by the study medication, and provided that the Investigator considers it is in the participant's best interest to be withdrawn. There must be a corresponding entry on the Adverse Events and/or the Serious Adverse Events Form in this instance.

Non-compliance:

The participant is withdrawn because of failure to comply with the treatment regimen, or comply with the investigations as required, but is still accessible to the Investigator.

Drop Out:

The participant withdraws consent to continue in the study, but the Investigator would otherwise consider it appropriate for him/her to continue. The participant remains accessible to the Investigator.

Lost to Follow-up:

The participant, without explanation, fails to keep appointments as scheduled for study assessments and is not seen again despite the Investigator's effort (letter, telephone, home visit etc.) to re-establish contact.

Death:

All deaths will be treated as Serious Adverse Events and Alliance Pharmaceuticals Ltd. must be informed within 24 hours. All associated documentation must be completed within 3 working days. Full details will be required including a post-mortem examination if possible.

Lack of Efficacy:

The participant elects to withdraw because the medication is not adequately effective.

Data from all participants will be collected and missing data will be imputed as described in section 3.4.

3. Analysis and Reports

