3.1.2 Efficacy

The primary outcome of the study is the proportion of individuals in each household with active head lice infestation at day 14.

Secondary objectives are:

To demonstrate the safety of Vamousse Lice Defence Shampoo in clinical use.

To demonstrate the acceptability of Vamousse Lice Defence Shampoo in daily use.

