3.3 Proposed Primary and Secondary Analyses

- 1. To compare the efficacy of Vamousse Lice Defence Shampoo with that of The Control Shampoo and to test for superiority in the intention-to-treat population.
- 2. To compare Vamousse Lice Defence Shampoo with The Control Shampoo in terms of safety.
- 3. To compare the cosmetic acceptability of Vamousse Lice Defence Shampoo with The Control Shampoo.
- 4. To compare the efficacy of Vamousse Lice Defence Shampoo with that of the Control Shampoo in the per-protocol population.

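### Acceptability is scheduled for collection only on Day 14, so participants who leave the study earlier have no planned rating on a stated secondary objective (minor).

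*Protocol*

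**What the plan says.** Acceptability is one of the aims in section 1.3. Section 3.1.2 lists it as a secondary objective: "To demonstrate the acceptability of Vamousse Lice Defence Shampoo in daily use". Section 3.3, item 3, makes it a between-arm analysis: "To compare the cosmetic acceptability of Vamousse Lice Defence Shampoo with The Control Shampoo". The analytical methods in section 3.4 include it among the variables to be tested between groups.

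On timing, Table 1 (Schedule of Events) has one row, "Collect User Acceptability Data", with a single mark under Day 14. No other section says when or how the ratings are obtained. Section 2.3.3.5 says of the Day 14 visit that "the investigator will conduct the final assessment, unless the participant is withdrawn sooner, i.e. they choose to withdraw or are withdrawn on safety grounds".

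Section 2.3.7 describes those who leave. For non-compliance it reads: "The participant is withdrawn because of failure to comply with the treatment regimen, or comply with the investigations as required, but is still accessible". For those who withdraw consent it adds: "The participant remains accessible to the Investigator". It closes with a general rule: "Data from all participants will be collected and missing data will be imputed as described in section 3.4". The only imputation rule in section 3.4 is last observation carried forward, stated in the context of the intention-to-treat analysis. The same section expects few drop-outs and continues recruitment until 84 families have completed.

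**The concern.** Dislike of a product that must be used every day is a plausible reason for leaving a 14-day study. If the rating is taken only from people present at the last visit, the reason for a missing rating can be the very thing being rated. The figure then describes those who found the shampoo acceptable enough to remain, together with those who stayed for other reasons, rather than everyone assigned to it.

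Two consequences follow. The level of acceptability in each arm tends to be overstated. The comparison between arms is also distorted if more people leave one arm out of dislike, because the less liked shampoo loses more of its unfavourable ratings. The two formulations differ in their listed ingredients (section 2.2.1), so unequal dislike is possible, though nothing in the protocol shows it. Unlike a choice of test or analysis set, a rating that was not taken cannot be recovered by a later analysis plan.

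**Working it through.** **Step 1: is there any route to a rating before Day 14?**

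- Table 1: acceptability is marked on Day 14 only.
- Section 2.3.3.5: the Day 14 assessment is not held for those withdrawn sooner.
- Section 2.3.3.4: the diaries record shampoo use and adverse events, not acceptability.
- Section 2.3.7: data from all participants are to be collected, but acceptability is not named and no time point is given for leavers.
- Section 3.4: carry-forward needs an earlier observation. None is scheduled, so there is nothing to carry.
- Section 3.4: replacing families that drop out adds further completers. It restores numbers, not the missing ratings.

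Followed as written, the plan schedules no rating for an early leaver.

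**Step 2: who is affected?** Only those who leave the study. Section 2.3.7 says participants may be withdrawn for non-compliance, so withdrawal is not automatic. Section 3.2 treats non-compliance as a per-protocol criterion, and section 3.4 keeps non-compliant households in the intention-to-treat analysis. A person who skips the shampoo but remains in the study is due at Day 14 and can be rated.

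**Step 3: how large could the effect be?** The protocol states no figure for acceptability, so there is none to reproduce. Let *p* be the proportion finding the shampoo acceptable among those asked at Day 14, and *w* the proportion of an arm that leaves early and is not asked. Both are assumptions. As an extreme case for given *p* and *w*, let every early leaver find the product unacceptable. Then:

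- acceptability in the whole arm = *p* × (1 − *w*)
- overstatement = *p* − *p* × (1 − *w*) = *p* × *w*

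| *w* | Whole arm, *p* = 0.80 | Overstatement | Whole arm, *p* = 0.90 | Overstatement |
|---|---|---|---|---|
| 2% | 0.80 × 0.98 = 0.784 | 1.6 points | 0.90 × 0.98 = 0.882 | 1.8 points |
| 5% | 0.80 × 0.95 = 0.760 | 4.0 points | 0.90 × 0.95 = 0.855 | 4.5 points |
| 10% | 0.80 × 0.90 = 0.720 | 8.0 points | 0.90 × 0.90 = 0.810 | 9.0 points |

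**Step 4: the arm comparison.** Suppose both arms show *p* = 0.90 at Day 14, with 2% leaving one arm and 5% the other, all for dislike. The observed difference is 0, whereas over all participants it is 88.2% − 85.5% = 2.7 points. With equal withdrawal in both arms and equal *p*, the comparison is not distorted.

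**The case against.** The strongest reply is that a Day 14 mark in Table 1 may be shorthand for the end of participation. Safety data and the completion form are also marked only on Day 14, yet adverse events are recorded throughout and the form is a Completion/Withdrawal Form. Section 2.3.7 says data will be collected from all participants and notes that non-compliers and drop-outs can still be reached. Drop-outs are expected to be few, the objective is secondary, and how to analyse missing ratings may properly be left to the statistical analysis plan.

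Much of this stands. It limits the size of the problem and rules out several stronger readings that a reader might infer:

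- *That everyone who stops the shampoo goes unasked, so only those who tolerated it answer.* Stopping the product is not leaving the study; those who stay are due at Day 14.
- *That the withdrawal form contains no acceptability question.* Neither the form nor the acceptability questionnaire is shown. One can say only that no such question is scheduled.
- *That an effect such as stinging would be filed as non-compliance or drop-out.* Section 2.3.5 treats unwanted effects as adverse events, and section 2.3.7 has an adverse-event withdrawal category.
- *That a difference between arms in stopping would go unseen.* Section 4.6 requires the numbers withdrawn and an explanation for each, and the diaries record use.

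What the reply does not remove is the gap itself. For adverse events and the form, the text extends collection beyond the Day 14 mark; for acceptability nothing does. That leavers can be reached makes asking them feasible, but no one is told to ask.

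**Conclusion.** The point holds in a limited form and is minor. As written, participants who leave before Day 14 have no scheduled acceptability rating, and the stated imputation rule cannot provide one. Acceptability may be somewhat overstated, and the between-arm comparison biased if withdrawal for dislike is unequal.

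The sizes in the table rest on assumed values of *p* and *w* and on every leaver disliking the product; the protocol supplies none of these. Since it expects few drop-outs, the low end is the more likely, at under 2 points for 2% withdrawal. The primary endpoint, its analysis and the sample size do not depend on acceptability.

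**What to change.** In Table 1 and section 2.3.3.5, state that the same acceptability questions are also asked at early withdrawal of participants who remain accessible and are willing to answer, together with the existing Completion/Withdrawal Form. State that these ratings enter the between-arm comparison.

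The cost is a few lines of text and one short questionnaire per withdrawal, with no change to sample size or treatment. Reported acceptability may be slightly less favourable. Participants lost to follow-up will still have no rating.

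A separate withdrawal reason for product dislike would be helpful but is optional, since each withdrawal must be explained in any case. Whether to count those who leave for dislike as finding the product unacceptable can be settled in the statistical analysis plan.
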